4.4.2.2 Quality of Life Analyses

The mean change in EuroQoL EQ-5D-5L Health Utility Index score from baseline to Week 24 will be computed by arm and compared.

4.4.3 Dose Reduction of Oral Corticosteroids and Immunosuppressants

A descriptive overview of background therapy dose reduction from OLE Week 12 onward will summarize the proportion of participants with an ongoing tapering or substantial dose reduction and/or discontinuation.

We consider the following ratios:

- Ongoing corticosteroid tapering: Number of participants who reduce their dose after OLE Week 12 and do not increase their dose subsequently, divided by number of participants who reduce their dose after OLE Week 12
- Successful corticosteroid tapering and discontinuation: Number of participants
 who either reduce their dose after OLE Week 12 to physiologic dose level of
 ≤7.5 mg prednisone daily dose equivalent or discontinue corticosteroid, divided
 by number of participants who reduce their dose after OLE Week 12
- Ongoing immunosuppressant (IST) tapering: Number of participants who reduce their dose after OLE Week 12 and do not increase their dose subsequently, divided by number of participants who reduce their dose after OLE Week 12
- Successful IST tapering and discontinuation: Number of participants who substantially reduce their dose after OLE Week 12 (at least 25% dose reduction) or withdraw from IST, divided by number of participants who reduce their dose after OLE Week 12

Of note: This analysis will be conducted on CCOD data set used for the primary analysis and will include only participants who have at least 24 weeks of OLE period data collected. The analysis will be repeated at the end of the study to provide a more complete picture.

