### 3.1.4 Open-Label Extension Period

Patients who complete the DB period can enter the OLE period. As of global protocol Version 5, adolescent patients will directly enter the OLE period after completion of screening (see Section 3.1.3). Patients who experience a clinical exacerbation that requires rescue therapy during the DB period may continue in the study until the end of the DB period and can enter the OLE period upon completion of treatment and assessments in the DB period.

For adult and adolescent patients who complete the DB period, the final visit of the DB period coincides with the Week 0 visit of the OLE period and is, therefore, considered the OLE baseline. The assessments performed at Week 24 of the DB period will be used as the active treatment baseline for the patients who receive placebo during the DB period and as the OLE baseline for patients who receive satralizumab during the DB period. Upon completion of the Week 24 assessments all patients will receive open-label treatment with satralizumab.

In the OLE period, all patients will receive open-label treatment with 120 mg or 180 mg satralizumab, as determined based on body weight. Patients who receive placebo during the DB period will receive satralizumab SC loading doses at Weeks 0, 2, and 4 in the OLE, followed by maintenance doses Q4W thereafter during the OLE period. Patients who receive active treatment during the DB period will continue receiving SC satralizumab Q4W during the OLE period but will receive an additional placebo SC injection at Week 2 to maintain blinding to DB treatment assignment.

For adult and adolescent patients who first enter the study randomized in the DB period, to ensure a period of satralizumab treatment stability in patients previously treated with placebo, dose reduction (taper) of background therapy (OCS, IST, and/or AChEls) can be started at or after Week 12 of the OLE period at the discretion of the investigator.

Adolescent patients who first enter the study in the OLE period will receive satralizumab SC loading doses at Weeks 0, 2, and 4 in the OLE, followed by maintenance doses Q4W thereafter.

Further details on adolescent patients in the OLE period are provided in Sections 3.1.3 and 3.4.8.

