#### 3.2 END OF STUDY AND LENGTH OF STUDY

The end of this study is defined as the date when the last patient, last visit (LPLV), occurs (i.e., last patient in the global study phase) or the date at which the last data point required for statistical analysis or SFU is received from the last patient (global enrollment phase), whichever occurs later. The LPLV is expected to occur approximately 2 years after the last patient in the global study phase enters the OLE period.

For adolescent patients enrolled directly in the OLE, the LPLV is expected to occur approximately 2.5 years after the last adolescent patient is enrolled in the adolescent OLE.

The end of the DB study period is expected to occur 24 weeks after the last patient in the global study phase is enrolled. The duration of the OLE period is estimated to be approximately 2 years from the last global study phase patient entering the OLE and approximately 4 years from the first patient entering this phase. The total length of study, from screening of the first patient to the end of the adolescent OLE period, is estimated to be approximately 6 years.

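### The ongoing-taper ratio in SAP 4.4.3 fixes no follow-up time after the dose reduction, so its values at the primary cut-off and at study end are not comparable

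*SAP*

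**What the plan says.** SAP Section 4.4.3 promises "A descriptive overview of background therapy dose reduction from OLE Week 12 onward" and lists four ratios, two for corticosteroids and two for immunosuppressants (IST). The ongoing-taper numerator is "Number of participants who reduce their dose after OLE Week 12 and do not increase their dose subsequently". The denominator is everyone in the data set with a reduction after that week. The IST version has the same wording. The two successful-taper ratios use the same denominator. They count those who reach 7.5 mg or less of prednisone equivalent daily or stop corticosteroids, and those who cut IST by at least 25% or stop it.

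On timing, the SAP says: "This analysis will be conducted on CCOD data set used for the primary analysis". The analysis "will include only participants who have at least 24 weeks of OLE period data collected". It then adds: "The analysis will be repeated at the end of the study to provide a more complete picture". There is no minimum time after the reduction, no fixed assessment time and no censoring rule.

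Under Protocol Section 3.1.4, for participants who entered through the double-blind period, a taper "can be started at or after Week 12 of the OLE period at the discretion of the investigator". Protocol Section 3.2 states: "The duration of the OLE period is estimated to be approximately 2 years from the last global study phase patient entering the OLE". It puts the OLE at about 4 years from the first entry.

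**The concern.** Whether a participant has increased again depends on how long they were watched after reducing, and the ratio ignores that time. A person who first reduces the day before the data cut and a person followed for a year with no increase each add one to the numerator and one to the denominator. The 24-week rule does not prevent this, because it counts from OLE entry. A participant at that minimum who reduced at Week 12 has at most 24 − 12 = 12 weeks of observation afterwards; one who reduced at the last visit has none.

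The ratio is then reported at two cuts with very different follow-up. Effect on steroid and IST dosing is a named OLE efficacy objective (Protocol Section 2, Table 3), and Protocol Section 3.4.8 treats lower steroid exposure as an important goal and promises prespecified taper analyses. The OLE has no control arm, so nothing offsets an artefact of the cut date.

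**Working it through.** The plan states no figure for this ratio, so there is nothing to reproduce. The check has four steps.

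**1. Same reducers, longer follow-up.** Let n1 people have reduced by the primary clinical cut-off date (CCOD), k1 of them with no later increase. If m of those k1 increase afterwards, the ratio for these people moves from k1/n1 to (k1 − m)/n1. It falls if m > 0 and is unchanged if m = 0; it cannot rise.

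**2. Open set of reducers.** Tapering may start at any time from OLE Week 12, and participants who pass 24 OLE weeks after CCOD become eligible. Suppose n2 new reducers join, a share s of them with no increase. The study-end ratio is (k1 − m + s·n2)/(n1 + n2). It is at least the CCOD ratio if and only if s ≥ k1/n1 + m/n2.

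Example: CCOD 7/10 = 70%. One of the seven then increases (6/10 in the original group), and 27 of 30 new reducers (90%) have no increase. Study end is (6 + 27)/40 = 82.5%. The threshold was 7/10 + 1/30 = 73.3%, so the ratio rises although the original group got worse.

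**3. Effect of follow-up alone.** Assume a constant hazard, with probability p of an increase within 24 weeks of the reduction (an assumption; range 5% to 30%). The expected share without an increase at t weeks is (1 − p)^(t/24), which is 100% at t = 0. The 92-week column is 104 − 12, for a person with 104 OLE weeks who reduced at Week 12.

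| p | 12 weeks | 24 weeks | 92 weeks |
|---|---|---|---|
| 5% | 97.5% | 95% | 82% |
| 10% | 94.9% | 90% | 67% |
| 20% | 89.4% | 80% | 43% |
| 30% | 83.7% | 70% | 26% |

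**4. The two cuts, simulated.** Protocol 3.2 gives about 4 years of OLE from first entry and 2 from last, so entry spans about 2 years. SAP Section 1.2 places the primary analysis when the last double-blind participants reach Week 24, which is about when they enter the OLE. I therefore assumed OLE follow-up uniform on 24 to 104 weeks at CCOD and 104 weeks more at study end. First reduction comes at 12 weeks plus an exponential time with mean 24 weeks (early tapering) or 80 weeks (slow). Study exits, and participants with under 24 OLE weeks at CCOD, were not modelled.

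| p | Tapering | CCOD | Study end, all reducers | Study end, CCOD reducers only |
|---|---|---|---|---|
| 5% | early | 92.1% | 75.4% | 73.6% |
| 5% | slow | 93.2% | 80.6% | 74.6% |
| 10% | early | 84.8% | 56.5% | 53.7% |
| 10% | slow | 86.6% | 65.0% | 54.9% |
| 20% | early | 71.1% | 30.7% | 27.0% |
| 20% | slow | 74.3% | 41.9% | 28.3% |
| 30% | early | 59.2% | 15.9% | 12.6% |
| 30% | slow | 63.5% | 27.4% | 13.6% |

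When re-increase was concentrated in those who reduced before OLE Week 40 (40% per 24 weeks, against 2% for later reducers, slow tapering), the overall ratio moved only from 66.4% to 62.8%, while the CCOD reducers fell to 37.6%.

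**The case against.** The SAP calls the ratio ongoing, which describes status at the data cut. It claims no durability, lists successful tapering separately, requires some OLE follow-up and presents the first run as incomplete by planning a second. It does not say the two values will be compared. The analysis is descriptive and exploratory, has no test and lies outside the hierarchy in SAP Section 4.3.7. All of that stands and limits the stakes. It does not answer the point: the entry rule guarantees no follow-up after the reduction, and the same ratio will still be reported twice on different follow-up, with nothing beside it to show the difference.

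A reader might go further and infer that the ratio is bound to fall at study end, and that the successful-taper ratios are bound to rise. The documents support neither. The set of reducers is open, so the ongoing ratio can rise, as step 2 shows. New reducers who have not yet met a success criterion can likewise pull the successful ratios down.

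**Conclusion.** The concern holds in limited form. The ongoing-taper ratio credits very recent reducers automatically, and the CCOD and study-end values estimate different quantities. The CCOD value tends to overstate maintenance over any period longer than the follow-up observed. For the same reducers the ratio can only stay level or fall; overall it may move either way, so neither a drop nor a rise between cuts can be read as a change in effect.

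No magnitude can be taken from the documents. Under a constant hazard of 5% or 10% per 24 weeks, with the assumed OLE follow-up and early tapering, the ratio goes from about 92% to 75%, or from about 85% to 57%, with unchanged behaviour. A fall was the usual simulated result, but it is not a necessary one. No confirmatory conclusion depends on this analysis.

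**What to change.** At both cuts, report time from the first reduction after OLE Week 12 to the first later increase by Kaplan-Meier, separately for corticosteroids and IST. Censor at the data cut or study exit, give estimates at fixed times after the reduction (for example 12, 24 and 48 weeks), and show the distribution of follow-up after reduction. Under the constant-hazard model the 24-week estimate targets 1 − p at either cut: 95% for p = 5% and 90% for p = 10%.

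Report the SAP's existing success criteria, unchanged, as cumulative incidence from first reduction at the same times, among reducers who did not already meet the criterion on the dose they were reducing from.

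The cost is SAP wording and minor programming. Section 4.4.2.1 already uses Kaplan-Meier with censoring, and the OLE schedule (Protocol Appendix 2) already records changes in background therapy. One drawback remains: censoring at study exit may be informative if people leave because they worsen, so exits after reduction should be tabulated with reasons.

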To assess the efficacy of satralizumab in the AChR+ population and OP	
 
Mean change from active treatment baseline in:         
 
MG-ADL total score
 
QMG score
 
MGC score
 
MG-QOL 15r score
 
 
 
Percentage of responders a based on:         
 
≥ 2-point reduction in total MG-ADL score or
 
≥ 3-point reduction in QMG score or
 
≥ 3-point reduction in total MGC score
 
 
 
Proportion of time and duration that patients show a meaningful improvement, defined as a ≥ 2-point reduction from active treatment baseline in total MG-ADL score
 
Number and severity of gMG-related exacerbations
 
	

 
To assess the effect of satralizumab on steroid/IST/AChEI dose modification in the AChR+ population and OP
 
	The proportion of patients who maintain clinical response without increase in symptomatic medication dose and are able to reduce corticosteroid dose or withdraw from corticosteroid or IST during the OLE	
Exploratory Efficacy Objective	Corresponding Endpoint	

 
To evaluate the efficacy of satralizumab versus placebo on additional QoL
 
	Mean change from baseline in Neuro–QoL Fatigue Subscale total score and EuroQoL EQ–5D–5L Health Utility Index score	

AChEI=acetylcholinesterase inhibitor; AChR=acetylcholine receptor; AChR+=AChR-antibody seropositive (patients/population); ADA=anti-drug antibody; AUC=area under the concentration—time curve; CL/F=apparent clearance;  $C_{trough}$ =trough concentration; IL-6=interleukin-6; IST=immunosuppressant; MG-ADL=Myasthenia Gravis Activities of Daily Living; MG-QOL 15r=Myasthenia Gravis Quality of Life 15 Scale (revised); NCI CTCAE v5.0=National Cancer Institute Common Terminology Criteria for Adverse Events, Version 5.0; Neuro-QoL=Quality of Life in Neurological Disorders; OLE=open-label extension; OP=overall population; PD=pharmacodynamic; PK=pharmacokinetic; QMG=Quantitative Myasthenia Gravis; QoL=quality of life; sIL-6R=soluble interleukin-6 receptor; V/F=apparent volume of distribution.

Table 3 Objectives and Endpoints during the Open-Label Extension Period (cont.)

Pharmacokinetic Objective	Corresponding Endpoints

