#### 3.4.8 Rationale for Open-Label Extension

Following the 24-week DB period, the study will include an OLE period of approximately 2 years from last patient in the global study. *Adolescent patients will be enrolled directly in the OLE after completion of screening (see Section 3.1.3)*. The objectives of the OLE are to evaluate satralizumab long-term safety and efficacy, including steroid/IST sparing, in patients with gMG.

The adolescent OLE aims to evaluate pharmacokinetics, pharmacodynamics, safety, and efficacy of satralizumab in adolescents aged  $\geq 12$  years to  $\leq 18$  years old with gMG.

This study will enroll patients on stable background therapy, including OCSs and ISTs as indicated in Section 3.1.

Long-term steroid treatment is associated with numerous adverse effects on many organ systems, including bone (osteoporosis, avascular necrosis), muscle (myopathy), metabolism and endocrine organs (weight gain, impaired glucose tolerance, hypothalamic-pituitary-adrenal suppression), skin (skin atrophy, acne, striae), eyes (glaucoma, cataract), behavior and mood (mood disorders, insomnia), cardiovascular system (hypertension, fluid retention, perturbations of serum lipoproteins), GI system (gastritis, peptic ulcer disease), and immune system (increased risk of infection). One of the key treatment goals in MG is to reduce exposure to steroids (Sanders et al. 2016; Jaretzki et al. 2000). The adverse event profile of the steroid-sparing ISTs that constitute the background therapy in this study includes renal toxicity with the use of cyclosporine, myelosuppression, infections, liver toxicity, and malignancies (Vodopivec et al. 2014; Collins et al. 2019)

At or after Week 12 of the OLE, tapering of steroids and IST background treatment will be allowed based on clinical judgement *for adult and adolescent patients randomized in the DB period at study start.* Satralizumab dosing until Week 12 of the OLE is required to ensure that patients treated with placebo during the DB period have reached steady-state satralizumab concentrations.

Adolescent patients enrolled directly in the OLE will remain on stable background therapy until Week 24 of the OLE period.

The ability of patients to successfully taper steroids or ISTs while concurrently taking satralizumab will be evaluated in the OLE period based on analyses that will be prespecified in the statistical analysis plan (SAP).

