1. INTRODUCTION

This Statistical Analysis Plan (SAP) details the planned analyses and considerations of statistical methodology for Study WN42636. Study WN42636 is a Phase III, randomized, placebo-controlled, double-blind, multicenter clinical study to evaluate the efficacy, safety, pharmacokinetic (PK), and biomarker effects of satralizumab in participants with generalized Myasthenia Gravis (gMG). For background information about the study, please refer to the Study Protocol WN42636. The analyses described in this SAP will supersede any analysis described in the Protocol for regulatory filings.

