4.1 GENERAL CONSIDERATION

In addition to specific analyses and presentations that are detailed in the following sections, study results will be presented by treatment arm (with total when appropriate) and summarized according to the nature of the variables.

For continuous variables, using descriptive statistics, including the number of participants contributing to summary statistics, mean, standard deviation, median, and range as appropriate.

For categorical variables, using the frequency and proportion of participants falling into each category, grouped by treatment arm (and total). The percentages given in these tables will be rounded and therefore may not always sum to 100%. If a missing category is not presented in the data display, only participants with non-missing values for the parameter being assessed will be included in the percentage calculation.

All efficacy analyses will be performed on the mITT (or subpopulations of the mITT) unless otherwise specified. If additional subpopulations are specified (i.e. AChR+ or AChR-), then the mITT restricted to those subpopulations will be analyzed. The mITT ensures that each participant is able to contribute a minimal meaningful amount of information to evaluate the treatment effect of satralizumab. The ITT and mITT exclude adolescents joining the study after the last adult participant is randomized. Adolescent participants not part of the mITT will be analyzed separately.

The primary efficacy analysis will be performed on the AChR+ participants. Participants will be analyzed according to the treatment assigned at randomization by the IxRS.

All safety analyses will be performed in the safety-evaluable population, unless otherwise specified. Participants will be analyzed according to the first treatment they received after randomization.

The baseline value will be defined as the last available value recorded prior to the initiation of study treatment, unless otherwise specified.

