4.4.1 Sustained Efficacy

To demonstrate evidence of sustained efficacy of satralizumab, the mean change from baseline to OLE Week 48 will be fitted using an MMRM for both the MG-ADL and the QMG in OP, AChR+ and AChR- participants. This analysis will include participants who at the time of the clinical cutoff (CCOD) have been enrolled for at least 40 weeks, i.e. with at least an OLE Week 16 visit for those still part of the study.

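### SAP 4.4.3 does not estimate the protocol's OLE steroid/IST-sparing endpoint: its four ratios cover only patients who tapered and ignore clinical response and symptomatic medication

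*SAP*

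**What the plan says.** Protocol Section 2, Table 3, lists this among the OLE efficacy objectives, apart from the exploratory one: "To assess the effect of satralizumab on steroid/IST/AChEI dose modification in the AChR+ population and OP". The endpoint is a share of patients, defined by this condition: "maintain clinical response without increase in symptomatic medication dose and are able to reduce corticosteroid dose or withdraw from corticosteroid or IST during the OLE". Protocol 3.4.8 leaves the taper analyses to the SAP.

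SAP 4.4.3 opens by saying that a descriptive overview "will summarize the proportion of participants with an ongoing tapering or substantial dose reduction and/or discontinuation". It then defines four ratios, two for corticosteroid and two for IST. The ongoing ratios count reducers with no later increase. The successful ratios count reducers who reach 7.5 mg prednisone equivalent or less, or stop (corticosteroid), and reducers with at least a 25% cut, or who stop (IST). Every one is "divided by number of participants who reduce their dose after OLE Week 12". The analysis takes only participants with at least 24 weeks of OLE data and is to be repeated at the end of the study.

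On populations, SAP 4.1 sets a default: "All efficacy analyses will be performed on the mITT (or subpopulations of the mITT) unless otherwise specified". SAP 4.4.1, the other OLE analysis, names its populations: "for both the MG-ADL and the QMG in OP, AChR+ and AChR- participants". On precedence, SAP Section 1 states: "The analyses described in this SAP will supersede any analysis described in the Protocol for regulatory filings".

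**The concern.** The protocol endpoint asks how many patients could cut back background immunosuppression while staying well and without leaning harder on symptomatic drugs. SAP 4.4.3 answers something narrower: among patients whose dose was cut, how often the cut lasted or went deep. The clinical conditions that give the protocol endpoint its meaning have dropped out, and AChEI, which the objective names, does not appear in the section.

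At stake is the reading of the OLE. A high successful-taper figure could be taken as evidence of steroid sparing with disease control, although nothing in it refers to disease control. No other SAP section supplies the composite. SAP Table 1 lists no OLE efficacy objectives, and its footnote on endpoints to be presented separately therefore does not cover this one.

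**Working it through.** The documents state no sample size, rate or precision for this endpoint, so there is no figure to reproduce. The check compares definitions.

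| Element | Protocol Table 3 | SAP 4.4.3 |
|---|---|---|
| Denominator | Patients, in AChR+ and OP; not fixed further | Those who reduced after OLE Week 12 (4 of 4 ratios) |
| Response kept | Required | Absent (0 of 4 include it) |
| No rise in symptomatic medication | Required | Absent (0 of 4 include it) |
| Corticosteroid | Reduced or stopped | Reduced with no later increase; or to 7.5 mg or less, or stopped |
| IST | Stopped | Reduced with no later increase; or cut by at least 25%, or stopped |

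**One patient traced through.** A participant cuts corticosteroid to 7.5 mg or less after OLE Week 12, then loses response or needs more AChEI. Under the protocol endpoint this patient does not count. Under the SAP's successful-corticosteroid ratio the patient is in both numerator and denominator. The two successful ratios also do not require the absence of a later dose increase; only the two ongoing ratios do.

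**Why the composite cannot be recovered.** Let N be the number on corticosteroid at the start of the permitted taper period, T the number who then reduce or stop, H the number of those with no later increase, and r the share of the T who keep response with no rise in symptomatic medication. Then:

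- SAP ongoing ratio = H / T
- Protocol-type proportion = (T × r) / N

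The first contains neither N nor r. Even with T known, the second needs r, which no part of SAP 4.4.3 produces.

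**Illustration, with every input assumed.** N = 100, r from 0.5 to 1.0, and H / T held at 80%.

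| Taperers T | SAP ongoing ratio | Protocol-type proportion |
|---|---|---|
| 10 | 8/10 = 80% | 10 × 0.5 / 100 = 5% to 10 × 1.0 / 100 = 10% |
| 50 | 40/50 = 80% | 50 × 0.5 / 100 = 25% to 50 × 1.0 / 100 = 50% |
| 100 | 80/100 = 80% | 100 × 0.5 / 100 = 50% to 100 × 1.0 / 100 = 100% |

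The proportion here does not require the taper to hold, because the protocol endpoint asks only that patients are able to reduce. N = all users is one possible denominator; the protocol does not settle it.

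**The case against.** Several points on the other side are fair.

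- **The number of taperers would probably be visible.** SAP 4.1 asks for frequency as well as proportion for categorical results, and the denominator of each pair of ratios is the count of reducers. Background medication use is also summarised at baseline (Protocol 6.3). A reader might infer that the SAP hides how many patients tapered; the documents do not support that. An unconditional taper proportion could be approximated, though not exactly, because 4.4.3 keeps only participants with 24 weeks of OLE data. What stays out of reach is how many taperers stayed well.
- **The opening sentence of 4.4.3 can be read as unconditional.** That is possible, but the ratios that make it concrete are conditional.
- **The protocol fixes no denominator, response definition or assessment time.** True, so any remedy involves choices. It does not excuse leaving out the two clinical conditions, which the protocol does state.
- **Appendix 1.** A reader might infer an undeclared change to a planned analysis, since Appendix 1 of the SAP does not mention tapering. Protocol Section 6 specifies no analysis of this endpoint, and 3.4.8 defers it to the SAP. What exists is an incomplete delegated analysis, not a separate defect.
- **Populations.** The mITT default in effect covers the OP, and about 160 of 185 planned patients (86%) are AChR+. The missing AChR+ split is minor.
- **Other OLE endpoints are also thinly covered**, for example OLE responders. That is so, but it does not supply this analysis.
- **The section is exploratory, descriptive and uncontrolled**, and never claims to estimate the composite. This limits the weight of the point but does not remove it.

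**Conclusion.** The point holds. As written, the SAP gives this protocol OLE endpoint no analysis that estimates it: all four ratios are conditional on a dose reduction, and none carries the response or symptomatic-medication condition. That rests on the text alone. The size rests on assumed inputs: the same 80% ongoing ratio is compatible with anything from 5% to 100% on a protocol-type proportion, depending on how many of 100 users taper and how many of those stay well.

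Two stronger readings should be resisted. One is that the four ratios are wrong: they are valid descriptions of tapers that were started. The other is that the trial's conclusions are exposed: the analysis lies outside the testing hierarchy, and neither the primary result nor type I error is touched. The change is worth making because it lets the OLE answer its own stated question at low cost.

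**What to change.** Add to SAP 4.4.3, for AChR+ and OP, the proportion of participants on corticosteroid (respectively IST) at the start of the permitted taper period who reduce or stop corticosteroid (respectively stop IST), with clinical response maintained and no increase in symptomatic medication dose. State the denominator, response definition and assessment time as choices made in the SAP. The protocol's OLE responder threshold, a reduction of at least 2 points in MG-ADL from active treatment baseline, is one available response definition. Report the number on each drug and the number who started a taper. Keep the four present ratios as supplementary.

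No new data are needed: Protocol Appendix 2 already schedules the response scales, concomitant medications and changes in background therapy during the OLE. The cost is three definitions and a little table programming, and the reported proportions will usually be lower. Two limits belong beside the result. Tapering is at the investigator's discretion (Protocol 3.1.4), so the proportion partly reflects willingness to taper. After OLE Week 24 the response scales are scheduled only every 24 weeks, so maintained response is measured coarsely.

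### The SAP's *successful* taper ratios lack a no-later-increase condition, and the steroid ratio also lacks a starting-dose condition, so they can count reversed tapers and further cuts from an already low dose as successes

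*SAP*

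**What the plan says.** SAP 4.4.3 sets out "A descriptive overview of background therapy dose reduction from OLE Week 12 onward" as four ratios, two for corticosteroids and two for ISTs. All four divide by those who reduced their dose after OLE Week 12.

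- **Ongoing (corticosteroid and IST):** "Number of participants who reduce their dose after OLE Week 12 and do not increase their dose subsequently".
- **Successful, corticosteroid:** the numerator is those "who either reduce their dose after OLE Week 12 to physiologic dose level of" 7.5 mg/day prednisone equivalent or less, plus those who stop; the denominator is as above.
- **Successful, IST:** a dose cut of at least 25%, or withdrawal, over the same kind of denominator.

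The analysis at the clinical cut-off date (CCOD) "will include only participants who have at least 24 weeks of OLE period data collected". It is then to be redone: "The analysis will be repeated at the end of the study to provide a more complete picture". The SAP does not say that the 24-week restriction is lifted for the repeat.

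On starting doses, Protocol 4.1.1 asks only that oral corticosteroids (OCS) have been taken for at least 3 months and at a stable dose for at least 4 weeks. Protocol 4.3.2.3 caps them at 30 mg/day. Neither sets a minimum. Protocol 3.4.8 names steroid and IST sparing among the OLE objectives and leaves it to the SAP to prespecify how successful tapering is evaluated.

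**The concern.** A ratio labelled *successful* tapering should separate participants who were brought down to the threshold and kept there from those who were not. As written, it does not. A participant already at or below 7.5 mg who takes any further cut is a success by construction. A participant who touched 7.5 mg and was then put back up remains a success. The phrase "and do not increase their dose subsequently" stands in the neighbouring *ongoing* definitions, so its absence from the *successful* ones changes who is counted.

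These two ratios are the SAP's only measure of tapering success. A reader of the study report would reasonably take them to mean a reduction that lasted.

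**Working it through.** **No planned figure to reproduce.** The documents state no expected taper rate, sample size or dose distribution for this analysis. The check is therefore a reading of the definitions, followed by an illustration on assumed inputs.

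**Step 1. Apply the corticosteroid rules to typical courses after OLE Week 12.**

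| Course | In denominator | Successful | Ongoing |
|---|---|---|---|
| From above 7.5 mg to 7.5 mg or less, held | yes | yes | yes |
| From above 7.5 mg to 7.5 mg or less, later raised again | yes | **yes** | no |
| Already at or below 7.5 mg, cut further (say 7 to 6 mg), held | yes | **yes** | yes |
| Already at or below 7.5 mg, stops completely | yes | yes | yes |
| Already at or below 7.5 mg, unchanged | no | no | no |
| Reduces, but has under 24 weeks of OLE data | excluded | excluded | excluded |

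The two bold cells are the gaps. For ISTs the success rule is a percentage cut, so the low-starting-dose problem does not arise. The reversal problem does.

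**Step 2. Direction.** Among reducers, let

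- f = share already at or below 7.5 mg,
- p = success share among those starting above 7.5 mg,
- r = share of counted successes whose dose is later raised.

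SAP ratio = f + (1 − f)p. 
Ratio among starters above 7.5 mg, with no later increase = p(1 − r). 
Difference = f(1 − p) + pr.

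Both terms are zero or positive, so each gap can only raise the ratio or leave it unchanged.

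**Step 3. Size on assumed inputs.** None of f, p or r is in the documents. The ranges assumed are f from 0 to 40%, r from 0 to 30%, and p at 40% or 60%.

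| p | f | r | SAP ratio | Strict ratio | Gap (points) |
|---|---|---|---|---|---|
| 0.40 | 0 | 0 | 0.40 | 0.40 | 0 |
| 0.40 | 0.20 | 0.20 | 0.20 + 0.80 × 0.40 = 0.52 | 0.40 × 0.80 = 0.32 | 20 |
| 0.40 | 0.40 | 0.30 | 0.40 + 0.60 × 0.40 = 0.64 | 0.40 × 0.70 = 0.28 | 36 |
| 0.60 | 0.20 | 0.20 | 0.20 + 0.80 × 0.60 = 0.68 | 0.60 × 0.80 = 0.48 | 20 |
| 0.60 | 0.40 | 0.30 | 0.40 + 0.60 × 0.60 = 0.76 | 0.60 × 0.70 = 0.42 | 34 |

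The f term treats every low-dose reducer as an uninformative success, including those who stop steroids altogether. The upper end is therefore generous to the concern.

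**Step 4. The 24-week data rule.** Because the denominator is reducers only, the rule affects the ratio only through people who had already reduced and have under 24 weeks of OLE data. Take the 52% case and add back 10 such people per 100 retained reducers, with success share s:

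(100 × 0.52 + 10s) / 110 = 47% at s = 0, 52% at s = 0.5, and 56% at s = 1.

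The rule can move the ratio either way.

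**The case against.** The strongest reply is that little hangs on this. The summary is descriptive, no test or between-arm comparison is specified, it lies outside the testing hierarchy in SAP 4.3.7, and the OLE has no control group. The *ongoing* ratio stands beside the *successful* one on the same denominator and already shows how often doses went back up. All of that is true and it limits the weight of the point. It does not close the gap, because the *ongoing* ratio does not show how many of the *successful* participants were later put back up.

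Three stronger readings are tempting, and the documents do not support them.

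- **That the steroid-sparing result is overstated.** The rule allows upward bias. Whether any occurs depends on starting doses and re-escalation, which the documents do not give. No inflation at all is within the range.
- **That everyone already at or below 7.5 mg counts as a success.** They count only if they reduce further or stop. Stopping from a low dose is a real withdrawal, and the OLE endpoint in Protocol Table 3 credits withdrawal with no dose floor. Simply removing low-dose participants would discard genuine results.
- **That the 24-week rule inflates the ratio.** It drops successes as well as failures, and it also drops people who are merely short of follow-up at the CCOD. Counting every early leaver as a failure would bring non-reducers into a reducers-only ratio and could bias it downward.

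**Conclusion.** The point holds as a gap in definition. The *successful* corticosteroid ratio lacks both a starting-dose condition and a no-later-increase condition; the *successful* IST ratio lacks the second. Both gaps act in one direction only, upward or not at all. The size cannot be determined from the documents: it is 0 to 36 points with p = 40% and 0 to 34 points with p = 60%, for f up to 40% and r up to 30%, all of them assumed. The exclusion of participants with under 24 weeks of OLE data is a separate weakness with no fixed direction and should not be added to that range. The matter is minor. It concerns how a descriptive figure is defined and read, and it leaves the primary and confirmatory analyses untouched.

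**What to change.** Amend SAP 4.4.3 as follows, keeping its own thresholds and changing no treatment rule.

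1. Add the no-subsequent-increase condition already used in the *ongoing* ratios to both *successful* ratios, applied up to the last available assessment.
2. Compute the component for reduction to 7.5 mg/day or less among reducers who were above 7.5 mg/day at OLE Week 12. Report complete discontinuation separately, for all OCS users whatever their starting dose.
3. Select participants who entered the OLE at least 24 weeks before the CCOD, in place of those with 24 weeks of data collected. SAP 4.4.1 already selects by time enrolled and requires the later visit only of those still in the study. Show reducers who left before OLE Week 24 as their own category, neither dropped nor all counted as failures. State that the same rule applies to the end-of-study repeat.

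The cost is SAP wording and a few more descriptive rows. Items 1 and 2 may lower the reported proportion; item 3 may move it either way.
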